# 7.9.6 Post-Treatment Follow-Up

- Physical examination every 12 weeks (+/- 7 days) for 12 months or until disease progression, whichever is sooner.
- Disease evaluation using ACTG criteria every 12 weeks (+/- 7 days) for 12 months (see Appendix 1), with clinical photographs every 12 weeks (+/- 7 days and on disease response or progression for 12 months or until progression, whichever is sooner.
- If visceral or extensive disease was identified at baseline, CT scans should be done every 12 weeks for 12 months post end of treatment, or until progression, whichever is sooner.

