# 2.1.2 Secondary Objectives

- To describe the pharmacokinetics of selumetinib in combination with HAART, including the effects of selumetinib on HAART metabolism.
- To assess the toxicity of selumetinib in combination with HAART.
- To describe the pharmacodynamic effects of selumetinib in combination with HAART.
- Progression free survival rate at 6 months from commencing treatment.

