#### 2.2.2 Phase I & II

- Toxicity assessed by CTCAE v 4.0 criteria (see Appendix 4).
- Number of selumetinib cycles completed and PFS data will be collected as supportive data out to
   12 months from the last patient completing study treatment.
- Objective response rates assessed using ACTG criteria (see Appendix 1).
- Progression free survival rate 6 months from the start of study treatment assessed using ACTG criteria.
- Human immunodeficiency virus (HIV) control by HIV-1 viral load pre-treatment and weeks 3, 6, 12 and 18, and CD4 counts pre-treatment and at weeks 9 and 18.
- Pharmacodynamic measures of selumetinib in combination with HAART assessed by:
  - Serum concentrations of angiogenesis markers including serum Ang-2, IL-6 and VEGF assessed by ELISA pre-study and on weeks 3, 6, 12 and 18.
  - Biopsies pre-study and at week 6 to assess pERK levels in tumour tissue and other downstream markers including c-myc, c-fos, changes in apoptosis markers such as Bad and Bcl-2, and adaptive changes in PI3K/Akt and other MAPK pathways such as JNK and p38.
- Analysis of peripheral blood mononuclear cells (PBMCs) collected in a sub-study at selected centres pre-treatment and at weeks 9 and 18.
  - Levels of pERK, down-stream targets c-fos and c-myc, and key apoptotic proteins Bad and Bcl-2 will be assessed by Western blotting of lysed viable PBMCs.
  - PBMCs will be challenged with TLR4 and 9 agonists and production of IL-1 $\beta$ , TNF- $\alpha$ , IL-6, IL-10, IL-12 and type 1 interferon will be measured by cytometric bead array of culture supernatants.
  - o ROS production by PBMCs will be measured by flow cytometry using dichlorofluorescein (DCF) and cell survival assessed by Annexin V-PE/TO-PRO3 staining and flow cytometry.

Page 18 of 61

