### 7.2 Treatment Schedule

Six cycles, each of 21 days, will be given unless disease progression or unacceptable toxicity is encountered. Patients who are responding after six cycles of selumetinib will be offered the option of continuing on selumetinib in combination with HAART. Patients who have had no disease progression and have been shown to derive benefit from the selumetinib and HAART combined therapy at one year should be continued on this regimen in an extension of the study as long as their risk: benefit analysis, in the opinion of the Chief Investigator and treating physician, favours the continuation of treatment and with approval from AstraZeneca. However, if after one year there is disease progression, treatment

should be discontinued and the patient should come off study. It should be noted that there is no compassionate use or access to selumetinib once off study.

Patients may also discontinue protocol therapy in the following instances:

- Intercurrent illness which would in the judgment of the investigator affect patient safety, the ability to deliver treatment or the primary study endpoints
- Request by patient

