# Additional Assessments:

- Tumour biopsy End of Cycle 2 (+/- 1 day).
- Disease evaluation on Cycle 2 Day 22/Cycle 3 Day 1, Cycle 4 Day 22/Cycle 5 Day 1 and Cycle 6 Day 22 then at the end of every 2 cycles (all +/- 1 day) in patients continuing selumetinib using ACTG criteria (see Appendix 1), with clinical photographs.
- Echocardiogram or multi gated acquisition (MUGA) scan (measurement of LVEF) to be performed on Cycles 2 Day 22/Cycle 3 Day 1 and Cycle 4 Day 22/Cycle 5 Day 1 (both +/- 1 day). If a decrease of LVEF of >10% is observed, an additional assessment may be performed at the 30 Day Post-Discontinuation Visit (+/- 3 days) and every 6 weeks thereafter (+/- 7 days) whilst LVEF continues to remain >10% from baseline. Decreases in LVEF from baseline may be investigated according to the algorithm (Appendix 7).
- All new dyspnoea AEs or worsening of pre-existing dyspnoea AEs should be followed according to the dyspnoea algorithm (Appendix 8).
- Ophthalmologic exam to include slit lamp examination, measurement of visual acuity, assessment of visual fields, assessment of colour vision, and overall visual assessment – to be performed in patients experiencing visual disturbances whilst in the trial as clinically indicated (Appendix 9).
- CT imaging of assessable disease (where present) at the end of every 2 cycles (+/- 1 day).

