### 7.10.4 Frequency of Tumour Re-evaluation

Tumours (cutaneous, oral and visceral) will be re-evaluated every 6 weeks (+/- 1 day) during treatment. After 6 cycles of treatment responding patients will be offered the option of continuing selumetinib in combination with HAART. Following discontinuation of protocol treatment and the 30 Day Post-Discontinuation visit, patients who have not progressed will continue to be re-evaluated every 12 weeks (+/- 7 days) for up to 12 months.

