# 7.10.5 Date of Progression

This is defined as the first day when the ACTG criteria for PD are met.

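### No disease evaluation is tied to the 6-month PFS landmark: a patient who stops at cycle 6 is next scheduled at about week 30, so the reported rate is likely biased upward

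*Protocol*

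**What the plan says.** - **Endpoint.** Protocol 2.1.2 lists "Progression free survival rate at 6 months from commencing treatment" as a secondary objective. Section 2.2.2 has it assessed by ACTG criteria.
- **Treatment length.** Section 7.2: "Six cycles, each of 21 days, will be given unless disease progression or unacceptable toxicity is encountered". The same section adds: "Patients who are responding after six cycles of selumetinib will be offered the option of continuing on selumetinib in combination with HAART".
- **Evaluations on treatment.** Section 7.9.2.2, under the additional assessments: "Disease evaluation on Cycle 2 Day 22/Cycle 3 Day 1, Cycle 4 Day 22/Cycle 5 Day 1 and Cycle 6 Day 22". Patients who stay on drug beyond this are evaluated after each further pair of cycles.
- **Evaluations after treatment.** Section 7.9.6: "Disease evaluation using ACTG criteria every 12 weeks (+/- 7 days) for 12 months". Photographs are also requested when response or progression occurs, and CT, where applicable, follows the same 12-week interval. Section 7.10.4 words the start differently: "Following discontinuation of protocol treatment and the 30 Day Post-Discontinuation visit, patients who have not progressed will continue to be re-evaluated every 12 weeks".
- **Visits in between.** The table in 7.9.7 marks no disease evaluation under Off Study or under the 30-day visit, and 7.9.3 and 7.9.4 list none.
- **Dating.** Section 7.10.5 on the date of progression: "This is defined as the first day when the ACTG criteria for PD are met". No back-dating or interval rule is given.

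**The concern.** The 6-month landmark falls inside a 12-week interval in which a patient who stopped at cycle 6 has no scheduled evaluation. Most ACTG progression criteria in Appendix 1 need examination or measurement, so progression that arises in the gap will often be recognised only at the next visit and dated there. By then the patient has already counted as progression-free at 6 months. The error runs in one direction, and more patients would not remove it.

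Observation also depends on outcome. Responders who continue are seen at week 24, while patients with stable disease who come off drug are not seen until about week 30. At stake is the only efficacy measure among the secondary objectives.

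**Working it through.** **Plan's own figures.** The protocol states no expected rate, size or power for 6-month PFS. The only sized quantity is the Simon design in 13.1.2. With 16 then 25 patients, stopping at 1 or fewer responses and declaring activity at 5 or more, exact binomial calculation gives alpha 0.0951 and power 0.9030. The design reproduces, and this point does not touch it.

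**Calendar.**
- End of cycle 6: 6 x 21 = 126 days = week 18.
- Next evaluation for a patient who stops there: 126 + 84 = 210 days = week 30, with a window of weeks 29 to 31.
- If the clock starts at the 30-day visit: 126 + 30 + 84 = 240 days = week 34.3.
- Six months: 365.25 / 2 / 7 = week 26.1.
- Patients who continue: weeks 24 and 30.
- Earlier stoppers differ. A stop at week 12 gives an evaluation at week 24, and a stop at week 6 gives weeks 18 and 30.

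**Size, under an assumed model.** Take exponential PFS, S(t) = 0.5^(t/m), with m = 22 and 39 weeks, the chemotherapy medians quoted in 1.1. These are illustrations, not predictions for selumetinib.

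| | m = 22 | m = 39 |
|---|---|---|
| S(18) | 0.567 | 0.726 |
| S(24) | 0.469 | 0.653 |
| S(26) | 0.441 | 0.630 |
| S(30) | 0.389 | 0.587 |

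Let f be the share of patients progression-free at week 18 who stop then. If progression is found only at scheduled visits, the reported rate is f x S(18) + (1 - f) x S(24). The excess over S(26) is

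f x [S(18) - S(26)] + (1 - f) x [S(24) - S(26)].

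The bracketed differences are 0.126 and 0.029 for m = 22, and 0.096 and 0.023 for m = 39. If all responders (rate r) are progression-free at week 18 and all continue, f = 1 - r/S(18).

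| Case | f, m = 22 | Excess (points) | f, m = 39 | Excess (points) |
|---|---|---|---|---|
| All continue | 0 | 2.9 | 0 | 2.3 |
| r = 30% | 0.471 | 7.5 | 0.587 | 6.6 |
| r = 10% | 0.824 | 10.9 | 0.862 | 8.6 |
| All stop | 1 | 12.6 | 1 | 9.6 |

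Example for m = 22 and r = 30%: 0.471 x 0.126 + 0.529 x 0.029 = 0.075.

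If half of the progressions in the gap are caught between visits, the all-stop figures halve to 6.3 and 4.8 points.

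In 25 patients the scheduled-visit excess is 25 x 0.023 = 0.6 to 25 x 0.126 = 3.2 patients. The 90% confidence half-width for the rate is about 1.645 x sqrt(0.44 x 0.56 / 25) = 0.16.

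The model ignores deaths and early stoppers and gives stoppers and continuers the same hazard.

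**The case against.** The strongest reply is that the endpoint is secondary and only reported, with no hypothesis or threshold, and that the excess lies within the sampling error of 25 patients. In addition, 7.10.5 speaks of the first day the criteria are met, not of a visit. Photographs are requested at progression, and there is a 30-day visit with adverse event assessment at about week 22, where new oedema, itself a progression criterion, could be noticed. The estimator may also be set in the SAP, which is not shown.

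Most of this stands as a limit on size and severity. It does not close the gap. None of these contacts is a scheduled ACTG evaluation, and photographs do not show visceral progression. No estimator can supply an observation that was not made. With visits at weeks 18 and 30, interval-censored methods only bound the week-26 value, here between 0.389 and 0.567 (m = 22) or 0.587 and 0.726 (m = 39).

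Four stronger readings are tempting but not supported:

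- **That the reported rate is mostly an 18-week rate.** Responders may continue and are then seen at week 24. At a 30% response rate only about 47% to 59% of week-18 survivors would stop. The protocol gives no expected share.
- **That the rate is certainly too high by a known amount.** The amount depends on that share and on unscheduled detection.
- **That 57% against 44%, and 73% against 63%, describe cycle-6 stoppers.** They are whole-cohort rates if every week-18 survivor stops. Among stoppers alone the contrast would be 100% against 0.441/0.567 = 78%, or 0.630/0.726 = 87%.
- **That the protocol earmarks the 6-month rate for planning later trials.** Section 12 says this of data collected beyond 6 months, and 1.5.2 rests the next trial on objective response.

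**Conclusion.** The gap in the calendar is a fact of the document: week 18, then about week 30 (or 34), with the landmark at week 26. The upward direction follows whenever progression in the gap is first recognised at the next scheduled visit. The size is conditional. Under exponential PFS with medians of 22 and 39 weeks and detection at scheduled visits only, the whole-cohort excess runs from 2 to 3 points up to 13 or 10 points. It is about 7 points at the design's 30% response rate. A reader might infer a threat to the trial's main conclusion, but there is none: the primary outcome is best response up to the end of cycle 6, and the Simon decision does not use PFS. This is a cheap improvement to a descriptive secondary endpoint.

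**What to change.** In 7.9.6, 7.10.4 and the 7.9.7 table:

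- Require a disease evaluation at week 26 from the start of treatment (+/- 7 days) for every off-treatment patient not yet progressed, then every 12 weeks. State that 6-month status is read from this visit.
- For cycle-6 stoppers this replaces the week-30 visit. For earlier stoppers, keep any 12-weekly visit that falls due before week 26, so that no evaluation is delayed.
- Reconcile 7.9.6 and 7.10.4 on when the 12-week clock starts.
- For patients already past week 26, report the 18-week rate and treat the 6-month rate as bounded by the visits on either side of week 26.

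**Cost.** For a cycle-6 stopper one follow-up visit, with CT where applicable, moves about 4 weeks earlier. The visits fall at weeks 26, 38, 50 and 62 instead of 30, 42, 54 and 66, which is four either way within 12 months of stopping. A patient who stopped at week 12 is due at weeks 24 and 26. The windows meet at week 25, so one visit there serves both; otherwise one visit is added.

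**What remains.** Patients still on drug are last seen at week 24, which leaves at most the 2 to 3 points shown for that group.

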# 7.9.7 Phase II: Assessments Summary Table

	Screening		Pre- g treatment Day 1 (+/- 1 day)		2 22/Cycle 3 Day 1	Cycle 3 Day 22/Cycle 4 Day 1 (+/- 1 day)	Cycle 4 Day 22/Cycle 5 Day 1 (+/- 1 day)	Cycle 5 Day 22/Cycle 6 Day 1 (+/- 1 day)	Cycle 6 Day 22 (+/- 1 day)	Patients continuing Selumetinib (every 3 weeks, +/- 1 day)	Off Study	30-days post discontinuation Selumetinib (+/- 3 days)	Post treatment (every 12 weeks, +/- 7 days)
	Within 4 weeks	Within 2 weeks											
Physical													
History & physical examination		х	Х	Х	Х	Х	Х	х	х	х			х
Disease evaluation and clinical photographs		х			Х		Х		х	X (end of every 2 cycles)			х
ВР		Х	Х	Х	Х	Х	Х	Х	Х	Х			
ECG		Х											
Echocardiogram (ECHO)/multi- gated acquisition (MUGA) scan	Х				Х		Х				\$X	\$X	
Ophthalmologic exam	#X												
Haematology													
Full blood count		Х	Х	Χ	X	Х	Х	Х	X	X	Х		
Clotting Studies		X	Х										
Biochemistry													
Urea & electrolytes		Х	х	Х	x	X	X	Х	х	Х	Х		
Liver function tests		Х	Х	X	x	X	x	X	Х	X	Х	*X	
Calcium and phosphate		х	х	Х	×	×	×	Х	Х	Х	Х		
Radiology													
Chest X-Ray		Х											
СТ	Х				†X		†X		†X				†X

# **Phase II Assessments Continued**

Concomitant Medications

	Screening		Pre- treatment Day 1	Cycle 1 Day 22/Cycle 2 Day 1 (+/- 1 day)	Cycle 2 Day 22/Cycle 3 Day 1 (+/- 1 day)	Cycle 3 Day 22/Cycle 4 Day 1 (+/- 1 day)	Cycle 4 Day 22/Cycle 5 Day 1 (+/- 1 day)	Cycle 5 Day 22/Cycle 6 Day 1 (+/- 1 day)	Cycle 6 Day 22 (+/- 1 day)	Patients continuing Selumetinib (every 3 weeks, +/- 1 day)	Off Study	30-days post discontinuation Selumetinib (+/- 3 days)	Post treatment (every 12 weeks, +/- 7 days)
	Within 4 weeks	Within 2 weeks											
Other Investigations													
HIV-1 viral load		Х	Х	Х	Х		Х		Х	X (end of every 3 cycles)			
CD4 count		Х	Х			Х			х	X (end of every 3 cycles)			
Angiogenic serum biomarkers			Х	Х	X		х		x				
Tumour biopsy	Х				Х								
††PBMC Sub- study			х			x			х	X (end of every 3 cycles)			
Adverse Events													
Toxicity reporting	Monitor throughout the course of the study  Monitor throughout the course of the study												

PK – Pharmacokinetics; PBMC – Peripheral Blood Mononuclear Cell. \$ required in patients who have a drop in LVEF > 10% from baseline; # subsequent assessments to be performed in patients experiencing visual disturbances as clinically indicated;\* patients with AST, ALT or bilirubin value above ULN or baseline values at the time of the last dose of selumetinib; † required if visceral or extensive nodal disease identified on baseline CT; †† participating centres only.

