# 3.2 Phase II

Patients will be recruited in a single-arm study at the RPTD, in order to determine objective tumour response using AIDS Clinical Trials Group Oncology Committee (ACTG) criteria (see Appendix 1). Patients recruited to the RPTD during phase I will be included in the phase II study. KS will be evaluated using clinical photographs of target lesions and bi-dimensional measurements every 3 weeks and/or CT imaging of assessable disease sites every 6 weeks during treatment. As in phase I, patients who continue to respond to selumetinib following completion of 6 cycles of therapy will be offered the option of continuing selumetinib. Patients who have been shown to derive benefit from selumetinib and HAART combined therapy at one year should be continued on this regimen as long as there has been no disease progression and their risk: benefit analysis, in the opinion of the Chief Investigator and treating physician, favours the continuation of treatment and with approval from AstraZeneca. To continue treatment beyond 6 cycles sites should contact the SCART Trial Office as described in section 3.1. Patients' HAART regimen should not be changed for their first 3 months on the trial (i.e. until after the C4D22/C5D1 visit) unless clinically necessary. If deemed clinically necessary, sites should contact the SCART Trial office to facilitate discussion with the Chief Investigator and Clinical Co-Investigators.

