# 4 ELIGIBILITY

### 4.1 Inclusion Criteria

- HIV positive and established on a HAART regimen for ≥ 3 months.
- · Histologically confirmed KS
- Measurable disease according to ACTG criteria.
- Progressive cutaneous or nodal KS not requiring chemotherapy OR progressive KS following cytotoxic chemotherapy.
- Evidence of disease progression in the past 6 months. No anti-cancer treatment within one month prior to commencing trial treatment.
- Adequate haematological function:
  - o Haemoglobin ≥ 9 g/dL
  - Absolute neutrophil count ≥ 1.5 x 10^9/L
  - o Platelets ≥ 100 x 10^9/L
- Adequate hepatic function:
  - Serum bilirubin ≤ 1.5 x upper limit of normal (ULN), except if the patient is established on the anti-retroviral drug atazanavir (no upper limit) and has AST and ALT levels ≤ 2.5 x ULN
  - ALT ≤ 2.5 x ULN
  - o AST ≤ 2.5 x ULN
- Adequate renal function:
  - o Serum creatinine clearance > 50 ml/min (Cockcroft-Gault formula or 24 hour urine collection).
- Age ≥ 18 years.
- World Health Organisation (WHO) performance status ≤ 2.
- For selumetinib, women of child bearing age and child bearing potential MUST have a negative
  pregnancy test prior to study entry AND be using an adequate contraception method, which must
  be continued while on treatment and for at least 4 weeks after the study treatment has ended.
- Male patients must agree to use an effective contraception method while on treatment and for at least 16 weeks after the study treatment has ended (barrier contraception is recommended for all individuals living with HIV).
- Written informed consent.

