#### 13.2.2 Phase II

Phase II will investigate the efficacy of selumetinib in combination with HAART in patients with KS. Patients recruited to the recommended phase II dose in phase I will be included in phase II.

In order to keep the trial the trial size as small as possible a Simon two-stage design will be used for patient accrual.

Phase II will accrue up to a total of 25 response evaluable patients (including those from phase I). The primary outcome measure of phase II is best objective tumour response up to the end of the 6th cycle. Objective tumour response is as defined by the ACTG criteria (refer to appendix 1 for details). Both CR and PR will count as responses for the purpose of the primary outcome.

- Response rate will be estimated with 90% confidence intervals.
- Toxicity per cycle and dose intensity will be reported.
- Number of treatment cycles completed, duration of response and progression free survival at 6 months from commencing treatment will be reported
- Percentage inhibition of pERK in tumour tissue will be calculated and correlated with tumour response. Changes to downstream proteins, apoptotic pathways and adaptive changes to other MAPK pathways will be assessed.
- Percentage changes in serum angiogenic markers will be calculated and correlated with tumour response.
- Percentage changes in HIV-viral load and CD4 count will be calculated.

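### The phase II assessment table contradicts the text on CT: it narrows who is rescanned and shows no CT during continued treatment, so progression seen only on CT can be missed or dated late

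*Protocol*

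**What the plan says.** CT after baseline is fixed in several places in the protocol.

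- **7.9.2.2, Additional Assessments:** "CT imaging of assessable disease (where present) at the end of every 2 cycles (+/- 1 day". No end point at cycle 6 is given.
- **3.2:** "CT imaging of assessable disease sites every 6 weeks during treatment", joined to clinical photographs by and/or.
- **7.10.4:** "Tumours (cutaneous, oral and visceral) will be re-evaluated every 6 weeks (+/- 1 day) during treatment". This also has no cut-off at cycle 6.
- **7.9.7, summary table:** the CT row is marked at screening, at the end of cycles 2, 4 and 6, and post treatment. Every mark after screening carries †, and the footnote reads "required if visceral or extensive nodal disease identified on baseline CT". In the column for patients continuing selumetinib the CT cell is blank, while the disease evaluation row in that column reads "X (end of every 2 cycles".
- **7.9.6, repeated in substance in 7.11:** "If visceral or extensive disease was identified at baseline, CT scans should be done every 12 weeks for 12 months post end of treatment". The word nodal is absent here.

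Eligibility (4.1) admits "Progressive cutaneous or nodal KS not requiring chemotherapy OR progressive KS following cytotoxic chemotherapy", with no threshold for the extent of nodal disease. The primary outcome (13.2.2) is "best objective tumour response up to the end of the 6 th cycle", with CR and PR both counting. The same section reports duration of response and progression free survival at 6 months.

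Neither extensive nor assessable is defined, and nothing says whether text or table prevails.

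**The concern.** A site will often schedule visits from the summary table. If it does so here, it departs from the text in two ways. It does not rescan a patient whose nodal disease is assessable but not judged extensive. It also stops CT at the end of cycle 6 in patients who stay on treatment.

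Patients offered continuation are those still responding (3.2, 7.2). In them, progression at a nodal or visceral site that can be seen only on CT would be found late or not at all. Progression under Appendix 1 includes new sites of disease, and response duration runs to the date on which progression is objectively documented (7.10.7), so fewer scans mean later documented dates. The evaluation form in Appendix 1 also asks for visceral disease, if present, to be one of the marker lesions. The table schedules the evaluation for continuing patients but not the CT that would measure such a lesion.

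**Working it through.** **1. The plan's own figures.** Section 13.1.2 uses null and alternative response rates of 0.10 and 0.30, stops at 1 or fewer responses in 16, and declares activity at 5 or more in 25. With X1 ~ Bin(16, p) and X2 ~ Bin(9, p),

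Pr(active | p) = Σ (x = 2 to 16) Pr(X1 = x) · Pr(X2 ≥ 5 − x).

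- p = 0.10: 0.0951, within the stated 0.10. The probability of stopping early is 0.515.
- p = 0.30: 0.9030, meeting the stated 0.90.

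A search for the minimax design returns the same design. The sample size calculation is not in question.

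**2. Who is scanned, text against table.**

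| Disease on baseline CT | Period | Text (7.9.2.2) | Table (7.9.7) |
|---|---|---|---|
| Visceral, or nodal judged extensive | Cycles 1 to 6 | End of cycles 2, 4, 6 | Same |
| Assessable nodal, not extensive | Cycles 1 to 6 | End of cycles 2, 4, 6 | None |
| Visceral or assessable nodal | Continued treatment | End of cycles 8, 10 and so on | None |

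**3. Timing.** Cycles last 21 days (7.2), so cycle c ends at week 21c/7 = 3c.

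- Cycle 6: week 18. Cycle 8: week 24. Cycle 10: week 30.
- Six months: about 52/2 = week 26.
- Last CT before the landmark in a continuing patient: week 24 under the text (26 − 24 = 2 weeks before), week 18 under the table (26 − 18 = 8 weeks before).
- A patient who stops at cycle 6 is next due a follow-up CT at about 18 + 12 = week 30 under either version, so the discrepancy at the landmark is confined to continuing patients.

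**4. Direction.** Suppose progression first appears at a nodal or visceral site between weeks 18 and 24. Under the text it is an event by week 24. Under the table, unless it shows clinically, the patient counts as progression free at 6 months. The error runs one way: the 6-month rate and the duration of response both go up.

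**5. Primary endpoint.** Its window closes at week 18. From step 2, only the second row differs in that window, so only assessable nodal disease that is not extensive is exposed. One patient is 1/25 = 4 percentage points, and the decisions turn on 1 against 2 of 16 and 4 against 5 of 25. The number of such patients is not given. For scale only, suppose a share f of true responses went unrecorded, so that p = 0.30 × (1 − f):

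| f (assumed) | p | Pr(active) |
|---|---|---|
| 5% | 0.285 | 0.873 |
| 10% | 0.27 | 0.837 |
| 20% | 0.24 | 0.742 |

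Nothing in the protocol supports any particular f. The error could also run the other way, if unseen nodal progression left a false response on record.

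**The case against.** The best defence is that the text is explicit and the table is only a summary, so a careful site would follow 7.9.2.2. Several supporting points stand.

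- Section 3.2 joins photographs and CT by and/or, and 7.10.4 names neither CT nor nodes. Only 7.9.2.2 plainly sets the broader CT rule.
- The post-treatment wording in 7.9.6 and 7.11 may be shorthand for the table footnote, so there may be two conditions rather than three.
- CR and PR both count as response, so an unseen residual node that would turn a CR into a PR leaves the response rate unchanged.
- At the 6-month landmark the loss is one CT. Data beyond 6 months are described as supportive (section 12), and duration of response is only reported.

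These points limit the consequence but do not resolve the contradiction, since no order of precedence is given.

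A reader might also infer more than the protocol supports:

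- **That visceral response goes unmeasured.** It does not: visceral disease found at baseline is scanned at the end of cycles 2, 4 and 6 under both versions.
- **That visceral progression is not looked for at all in continuing patients.** Disease evaluation is still scheduled every 2 cycles. It is the CT mark that is missing.
- **That 4 to 20 percentage points of the response rate are at risk.** This takes 1 to 5 of 25 patients with limited nodal disease and assumes that every one changes responder status in the same direction. The protocol supports neither assumption.
- **That there is a 46-week gap in CT.** This arises only for an assumed patient treated to week 52 and first scanned 12 weeks later (52 + 12 − 18 = 46), and most of it falls in the supportive period.

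**Conclusion.** The contradiction is real and should be corrected. Table and text differ on who has CT after baseline and on whether CT continues beyond cycle 6. The main consequence is an upward bias in the 6-month progression free survival rate and in duration of response among continuing patients with visceral or nodal disease. At the landmark the difference is a last CT at week 18 instead of week 24.

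For the primary endpoint the exposure is narrow: assessable nodal disease that is not extensive, in numbers the protocol does not state. No effect on the response rate can be calculated, and the two-stage design is unaffected.

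This rests on two assumptions: that some sites work from the table, and that some progression in these patients is visible on CT but not clinically.

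**What to change.** Reconcile the passages by amendment:

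1. In 7.9.7, make the on-treatment † condition agree with the wording of 7.9.2.2, which covers assessable disease wherever it is present.
2. In the CT row of 7.9.7, enter CT at the end of every 2 cycles for patients continuing selumetinib, subject to the same condition, to match 7.9.2.2 and 7.10.4.
3. Use one wording for the post-treatment CT condition in 7.9.6, 7.9.7 and 7.11. Do not widen it: no passage now requires 12-weekly follow-up CT for every patient with any nodal disease. If the word extensive is kept there, define it.

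The cost is a correction to the table, its footnote and two short paragraphs. The on-treatment scans are already required by the text, so extra CT arises only at sites that have been following the table.
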